# LIST OF ABBREVIATIONS

AE	Adverse Event
CRF	Case Report Form
FDA	Food and Drug Administration
IMP	Investigational Medicinal Product
IRB	Institutional Review Board
LMWH	Low Molecular Weight Heparin
NOAC	New Oral Anticoagulant
NSAID	Non-steroidal anti-inflammatory drug
SAE	Serious Adverse Event
SAP	Statistical and Analytical Plan
TXA	Tranexamic Acid
VAS	Visual Analogue Scale
VKA	Vitamin K Antagonist

EXTRACT-NOAC Version 1.1
Protocol 5 July 2017

#### PROTOCOL SUMMARY

Tranexamic Acid To Reduce Bleeding in Patients Treated with New Oral

Anticoagulants Undergoing Dental Extraction

Acronym: EXTRACT-NOAC

**Précis:** Two hundred thirty-six patients treated with NOACs and scheduled for dental

extraction will be randomized to tranexamic acid mouthwash 10% or placebo: one administration before extraction and 3 times daily on day 1 till day 3 after

extraction. Bleeding events will be evaluated on day 2 and day 7.

**Objectives:** Primary objective: To evaluate whether TXA mouthwash reduces the number

of oral bleeding events in patients who undergo dental extraction and are

treated with NOACs .

Outcome: Primary outcome: Any oral bleeding (early or delayed; minor or clinically

relevant) from randomization till end of study follow-up)

Population: Patients treated with a NOAC, aged 18 years or older undergoing dental

extraction

Phase: Phase IV

Number of Sites enrolling participants:

2

Site 1: University Hospitals Leuven, Belgium Site 2: Ziekenhuis Oost-Limburg, Genk, Belgium

**Description of Study** 

Agent:

Tranexamic acid mouthwash (1g in 10ml, 10%) before extraction and 3 times

daily on day 1 till day 3 after extraction

Study Duration: 24 months

Participant Duration: 7 days

### SCHEMATIC OF STUDY DESIGN

Screening: inclusion and exclusion criteria. Obtain informed consent. Standard-of-care: No NOAC on the day of extraction.

# Inclusion and randomization: online platform

TXA group N=118 Placebo group N=118

Day of extraction

- Study intervention: perform mouthwash before extraction
  - Perform dental extraction
  - Physician records baseline patient demographics and procedure characteristics and sends form to study coordinator

Day 1 after extraction

- Restart NOAC
- Study intervention: mouthwash 3 times a day for 3 days

Day 2 after extraction

 Follow-up assessment of compliance and bleeding events by phone call

Day 7 after extraction

 Follow-up assessment of compliance, bleeding events and safety outcome by phone call

# 2 INTRODUCTION: BACKGROUND INFORMATION AND SCIENTIFIC RATIONALE

#### 2.1 BACKGROUND INFORMATION

Since the introduction of new oral anticoagulant drugs (NOACs), the number of patients treated with this class of antithrombotics is steadily increasing. For major surgical procedures, vitamin K antagonists (VKAs) are discontinued prior to the procedure and resumed thereafter. Temporary interruption of VKA treatment confers both an ischemic as well as bleeding risk. This is caused by complex pharmacokinetics during interruption, the long half-life of VKA, and concomitant bridging therapy with low molecular weight heparins (LMWH). Since there is no increased risk of major bleeding when performing minor procedures such as dental extractions on stable VKA treatment, it is current practice not to discontinue VKAs for dental extractions (1).

In contrast to VKA, little evidence is available for the periprocedural management of NOACs in dental extractions (2). The current guidelines of the European Heart Rhythm Association advise to perform dental extractions at trough level (3-6). However, in clinical practice it can be complicated to schedule the extraction at the time of the day corresponding to trough plasma levels.

We have therefore recently shown that a standardized pragmatic approach in patients who undergo dental extractions, by skipping only the dose on the morning of the extraction, regardless of timing of extraction, drug regimen or renal function, is feasible and safe (7). In a total of 52 patients, there was no difference in the procedural bleeding score or in early bleeding between NOAC patients and controls (patients without any antithrombotics). However, delayed bleeding between day 1 and day 7 occurred more frequently in anticoagulated compared to non-anticoagulated patients (7 versus none, p=0.01). Similarly, an increase in bleeding during the first postoperative week was reported in a retrospective study in patients undergoing dental extraction under uninterrupted NOAC treatment (8). The combination of peak plasma levels of the NOAC with an immature coagulum at the extraction site could trigger bleeding.

Since bleeding events can lead to unscheduled interruption of NOAC treatment and subsequent increased risk of thrombo-embolic events, an optimal strategy to minimize bleeding events after dental extractions is required. In this interventional phase IV study, we want to assess whether adding tranexamic acid (TXA) mouthwash reduces the number of bleeding events in patients treated with NOACs undergoing a dental extraction.

#### 2.2 RATIONALE

The aim of this study is to evaluate whether adding TXA 10% mouthwash to standard-of-care (i.e. performing the extraction at trough level by skipping the NOAC on the day of the extraction) will decrease the number of bleeding events.

TXA is an antifibrinolytic agent that reversibly inhibits plasminogen, preventing plasmin from degrading fibrin. Oral administration of TXA is approved in the United States by the FDA to prevent bleeding in patients with hemophilia undergoing dental extraction. To avoid any possible prothrombogenic effects in an unselected patient population or accumulation in case of renal insufficiency, there is increased interest in topical administration of TXA. It has been shown that upon systemic administration of 1g TXA, peak plasma levels reach 7µg/mL, whithout detectable levels in saliva. However, when administering a 10ml 5% TXA mouthwash, plasma levels remained low (below 2µg/mL) while the levels in saliva remained at therapeutic level for two hours (9). TXA mouth wash is therefore the suitable route of administration, and is considered safe without evidence for prothrombotic effects (10).

Two studies have shown that TXA 5% mouthwash during 7 days after dental extraction significantly reduces the number of bleeding events in patients treated with VKA (11, 12). A third study showed no difference between a 2-day TXA regimen compared to 5 days (13). In Belgium, 10% TXA mouthwash unidoses are commercially available in packages of 10 doses. Therefore, we opt to treat patients with 10% TXA mouthwash for 3 days, 3 times a day (9 doses) starting on the day after the dental extraction. In order not to mechanically dislodge the immature coagulum, there is no post-extraction mouthwash, but one additional mouthwash is performed immediately prior to the dental procedure.

The control group will receive a water solution, which does not confer any issues. All patients older than 18 years, treated with a NOAC and scheduled for dental extraction are eligible for inclusion.

#### 2.3 POTENTIAL RISKS AND BENEFITS

#### 2.3.1 KNOWN POTENTIAL RISKS

Potential risks of systemic administration of TXA, as reported by the package insert, include convulsions, blurred vision, haematuria and thrombo-embolism. However, none of these potential risks have been shown to be present in case of mouthwash as compared to systemic administration (10). This can be explained by the low systemic TXA levels in case of administration by mouthwash (9).

Therefore, the immediate potential risk of TXA mouthwash is limited to:

- Allergic reaction
- Bleeding in case of extensive or traumatic mechanical rinsing

There are no known long-term risks. Because of these limited potential risks, the potential benefit of this treatment is expected to outweigh the risks.

#### 2.3.2 KNOWN POTENTIAL BENEFITS

Local administration of TXA is known to reduce bleeding, resulting in immediate potential benefits:

- In patients on VKA treatment, TXA 5% mouthwash reduced the number of bleeding events (11, 12).
- In patients undergoing surgery, local administration of TXA significantly reduced the number of bleeding events (10).

Since a reduction of bleeding would possibly result in less unplanned discontinuation of the NOAC, a reduction in thrombo-embolic events caused by NOAC cessation can be expected, although the current study will not be powered to evaluate this long-term benefit.

#### 3 OBJECTIVES AND PURPOSE

#### Primary objective:

• To evaluate whether TXA mouthwash 10% reduces the number of oral bleeding events in patients treated with NOACs and undergoing dental extraction.

#### Secondary objectives:

- To evaluate whether TXA mouthwash before the extraction reduces the bleeding during the procedure.
- To evaluate whether TXA mouthwash reduces early and/or delayed bleeding events
- To evaluate whether TXA mouthwash reduces minor, clinically relevant or major bleeding events or reinterventions.
- To evaluate whether TXA mouthwash reduces the number of unplanned NOAC interruptions.
- To evaluate the safety of skipping the dose of the NOAC on the day of the extraction.

#### Exploratory analyses:

- To investigate the potential relationship between time of last NOAC dose administered prior to the extraction (regardless of specific NOAC type), time of resuming NOAC after the procedure, and bleeding events
- To investigate the potential benefit of TXA in subgroups of patients (molar versus non-molar extraction)

#### 4 STUDY DESIGN AND OUTCOMES

#### 4.1 DESCRIPTION OF THE STUDY DESIGN

This is a randomized, double-blind, placebo-controlled, multi-center phase IV clinical trial assessing the benefit of TXA mouthwash.

#### 4.2 STUDY OUTCOMES

The procedural bleeding score is a visual analogue score (VAS) ranging from 0 (no bleeding) to 10 (unstoppable bleeding).

A reintervention is defined as any procedure in the oral cavity for the treatment of bleeding, performed by any dentist or maxillofacial surgeon, except for rinsing the extraction socket with saline.

All suspected bleeding events and reinterventions will be adjudicated by a blinded adjudicator, unaware of the assigned treatment.

Bleedings are defined as previously published (7):

- Minor bleeding: any oral bleeding experienced by the patient that does not require medical contact.
   Eg. blood on the pillow, bleeding requiring the use of additional gauzes, clear red bleeding when spitting out the mouthwash
- Clinically relevant non-major bleeding: any oral non-major bleeding requiring unplanned medical contact (by phone or with any health care professional (dentist, general practitioner, maxillofacial surgeon), with or without re-intervention
- Major bleeding: any oral bleeding requiring blood transfusion, hospitalization or resulting in death
- Early bleeding: any oral bleeding occurring after the extraction up to and including day 1 after the extraction
- Delayed bleeding: any oral bleeding occurring between day 2 and day 7

#### 4.2.1 PRIMARY OUTCOME

• Any oral bleeding (early or delayed; minor or clinically relevant)

#### 4.2.2 SECONDARY OUTCOMES

- The procedural bleeding score
- Early and delayed bleeding
- Minor, clinically relevant non-major and major bleeding
- Clinically-relevant bleeding (non-major and major)

EXTRACT-NOAC Version 1.1
Protocol 6 July 2017

- The number of reinterventions
- The number of unplanned NOAC interruptions

#### Safety outcomes:

- Any non-oral bleeding
- All thrombotic events including myocardial infarction, stroke, systemic embolism and venous thrombo-embolism up to the endo of study follow-up.

#### 4.2.3 EXPLORATORY OUTCOMES

The following subgroup analyses are planned:

- Risk factor analysis for bleeding, eg. patient demographics and procedural characteristics
- The number of bleeding events in patients in relation to the time since stopping and resuming NOAC in relation to the dental extraction, e.g. in patients who stopped/resumed NOAC treatment within 24 hours prior/after extraction compared to more than 24 hours prior/after extraction.

#### 5 STUDY ENROLLMENT AND WITHDRAWAL

#### 5.1 PARTICIPANT INCLUSION CRITERIA

- Patients scheduled for dental extraction and treated with edoxaban, apixaban, rivaroxaban or dabigatran
- Not having taken the NOAC on the day of the extraction
- Provision of signed and dated informed consent form
- Stated willingness to comply with all study procedures and availability for the duration of the study
- 18 years or older

#### 5.2 PARTICIPANT EXCLUSION CRITERIA

- Subjects with any condition that as judged by the Investigator would place the subject at increased risk of harm if he/she participated in the study.
- Pregnancy or lactation
- Known allergic reaction to TXA

#### 5.3 STRATEGIES FOR RECRUITMENT AND RETENTION

All patients undergoing dental extraction at the outpatient clinic of the registered sites will be screened for eligibility before their dental extraction. Standard-of-care (discontinuation of the NOAC on the day of the procedure) is already implemented in the participating site. Adherence to the study protocol will be assessed by phone call on day 2 and day 7.

#### 5.4 PARTICIPANT WITHDRAWAL OR TERMINATION

#### 5.4.1 REASONS FOR WITHDRAWAL OR TERMINATION

Participants are free to withdraw from participation in the study at any time upon request. An investigator may terminate participation in the study if:

- Any clinical adverse event (AE), laboratory abnormality, or other medical condition or situation occurs such that continued participation in the study would not be in the best interest of the participant
- The participant meets an exclusion criterion (either newly developed or not previously recognized) that precludes further study participation.

#### 5.4.2 HANDLING OF PARTICIPANT WITHDRAWALS OR TERMINATION

When a participant is withdrawn from the study, planned follow-up by phone call will be continued, unless the patients does not provide consent to follow-up. However, all data collected prior to discontinuation from the study will be retained in the database.

#### 5.5 PREMATURE TERMINATION OR SUSPENSION OF STUDY

This study may be temporarily suspended or prematurely terminated if there is sufficient reasonable cause. Written notification, documenting the reason for study suspension or termination, will be provided by the suspending or terminating party. If the study is prematurely terminated or suspended, the PI will promptly inform the IRB and will provide the reason(s) for the termination or suspension.

Circumstances that may warrant termination or suspension include, but are not limited to:

- Determination of unexpected, significant, or unacceptable risk to participants
- Insufficient compliance to protocol requirements
- Data that are not sufficiently complete and/or evaluable

Study may resume once concerns about safety, protocol compliance, data quality are addressed

#### **6 STUDY AGENT**

#### 6.1 STUDY AGENT(S) AND CONTROL DESCRIPTION

#### 6.1.1 ACQUISITION

Blinded 10% TXA mouthwash or placebo will be manufactured in collaboration with the Center of Clinical Pharmacology, University Hospitals Leuven

#### 6.1.2 FORMULATION, APPEARANCE, PACKAGING, AND LABELING

- Active treatment: 10 doses of 10% TXA mouthwash 10ml, blinded, in oral syringes, labeled according to randomization scheme
- Placebo: 10 doses of 10ml water with addition of white cherry flavor, in oral syringes, labeled according to randomization scheme

#### 6.1.3 PRODUCT STORAGE AND STABILITY

Repackaged TXA 10% in 10ml oral syringes (Exacta-Med, Bayer) will be submitted for stability testing to Phasius, [name]. As backup, 100ml TXA 10% in glass bottles will be tested for stability (room temperature and refrigerated). Batches of 100 syringes (equivalent of 10 patients) will be delivered to the sites.

#### 6.1.4 PREPARATION

TXA 10% oral ampoules will be repackaged into blinded and labeled 10ml Exacta-Med oral syringes. For placebo, white cherry flavor will be added to water up to 10ml and packaged in blinded and labeled 10ml Exacta-Med oral syringes.

#### 6.1.5 DOSING AND ADMINISTRATION

- 10ml 10% TXA mouthwash before dental extraction
- 10ml 10% TXA mouthwash from day 1 until day 3, 3 times a day (morning, noon, evening)

#### 6.1.6 ROUTE OF ADMINISTRATION

10 ml mouthwash

#### 6.1.7 STARTING DOSE AND DOSE ESCALATION SCHEDULE

1g TXA in 10ml (10%) mouthwash

#### 6.1.8 DOSE ADJUSTMENTS/MODIFICATIONS/DELAYS

No dose adjustments

#### 6.1.9 DURATION OF THERAPY

Until and including day 3 after extraction.

## 6.1.10TRACKING OF DOSE

Adherence to study treatment will be assessed during the follow-up phone calls at day 2 and day 7.

#### 6.2 STUDY AGENT ACCOUNTABILITY PROCEDURES

TXA 10% mouthwash is used on-label in this study. A service level agreement between the investigators and manufacturing contractor will be made in agreement with good clinical, pharmacological and manufacturing practice.

#### STUDY PROCEDURES AND SCHEDULE

#### 7.1 STUDY PROCEDURES/EVALUATIONS

#### 7.1.1 STUDY SPECIFIC PROCEDURES

- Mouthwash: patients are instructed to gently rinse the mouth with 10ml of 10% TXA or placebo for 1 minute and to spit out the mouthwash thereafter.
- Patients will be given 9 vials of 10ml 10% TXA or placebo and instructed to rinse 3 times a day for 3
  days, starting the day after the procedure. Patients will be instructed to monitor and record bleeding
  events.
- Patients will be contacted be telephone call on day 2 and day 7, and the prespecified outcomes will be assessed.
- In case of unplanned medical contact, the prespecified outcomes will be assessed as planned by phone call, and in addition, additional relevant medical data on the type of unplanned medical contact will be identified from the medical file.

#### 7.1.2 STANDARD OF CARE STUDY PROCEDURES

- No NOAC dose is to be taken on the day of the procedure
- Dental extraction is then performed according to the current and local standard-of-care, at the discretion of the treating physician. The use of additional hemostatic measures is permitted but will be recorded.
- Patients will be instructed to restart the NOAC the day after the extraction, according to current standard-of-care.
- Any other antithrombotic medication is to be continued

#### 7.2 LABORATORY PROCEDURES/EVALUATIONS

Not applicable

#### 7.3 STUDY SCHEDULE

#### 7.3.1 SCREENING

- Review medical history and medication to determine eligibility based on inclusion/exclusion criteria (age and use of NOAC).
- Obtain informed consent of potential participant verified by signature on study informed consent form
- Randomize patient (investigator takes next batch of pre-randomized study medication)

#### 7.3.2 ENROLLMENT/BASELINE

- Assess patient characteristics:
  - o Age
  - Sex
  - Date of birth
  - Alcohol and tobacco use
  - Phone number for follow-up calls
  - NOAC type: rivaroxaban, apixaban, dabigatran, edoxaban
  - NOAC dose and regimen
  - NOAC indication
  - Date and time of last NOAC dose
  - Serum creatinine when available (up to 12 months before inclusion)
  - Other antithrombotic drugs: aspirin (Asaflow®, Cardio-aspirine®), clopidogrel (Plavix®), ticagrelor (Brilique®), prasugrel (Efient®), dipyridamole (Aggrenox®), LMWH
  - Non-steroidal anti-inflammatory drug use (eg. ibuprofen)
  - o Record full list of medication in the medical file
- Administer the study treatment
- Perform dental extraction
- Assess procedure characteristics:
  - o Date and time of extraction
  - Number of extracted teeth
  - Teeth numbers
  - Stitches: yes/no
  - Persistent infection: yes/no
  - Burring: yes/no
  - Procedural bleeding score (0-10)
  - o Use of additional hemostatic measures: eg. tranexamic acid gauze
  - o Prophylactic antibiotics: yes/no
- Instructions to patient:
  - Supply patient with 9 vials of mouthwash
  - Supply patients with instructions to perform mouthwash starting 1 day after extraction, 3 times a day for 3 days
  - Instruct patients to restart NOAC the day after the extraction according to their normal regimen
  - Instruct patients to write down any signs of bleeding

#### 7.3.3 FOLLOW-UP

Follow-up assessment on day 2 (phone call). In case this would be a Saturday, follow-up can be performed on Friday afternoon. In case this would be a Sunday, follow-up can be performed on Monday.

- Date and time of assessment
- Date and time of restarting NOAC
- Did patient use mouthwash day after the extraction: yes/no
- Bleeding assessment:
  - o Blood on pillow, additional gauze, other: yes/no
  - Blood when brushing teeth: yes/no
  - Blood when rinsing with mouthwash: yes/no
  - Date and time of bleeding
  - Unplanned medical contact (by phone, new consultation or hospitalization) with any health care professional (dentist, general practioner, maxillofacial surgeon): yes/no
- In case of unplanned medical contact:
  - o Date and time
  - Reason (adjudicated): bleeding infection death other (specify)
  - Treatment: no treatment oral antibiotics only rinsing with saline hemostasis with gauze - hemostasis with coagulation - removal of false coagulum - new sutures - blood transfusion - hospitalization
- Unplanned interruption of NOAC: yes/no
- AE and SAE assessment

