#### 7.3.4 FINAL STUDY VISIT

Follow-up assessment on day 7 (phone call). In case this would be a Saturday, follow-up can be performed on Friday afternoon. In case this would be a Sunday, follow-up can be performed on Monday.

- Date and time of assessment
- Number of used study drug vials
- Bleeding assessment between day 2 and day 7:
  - o Blood on pillow, additional gauze, other: yes/no
  - Blood when brushing teeth: yes/no
  - Blood when rinsing with mouthwash: yes/no
  - Date and time of bleeding
  - Unplanned medical contact (by phone, new consultation or hospitalization) with any health care professional (dentist, general practioner, maxillofacial surgeon): yes/no
- In case of unplanned medical contact:
  - Date and time
  - o Reason (adjudicated): bleeding infection death other (specify)
  - Treatment: no treatment oral antibiotics only rinsing with saline hemostasis with gauze - hemostasis with coagulation - removal of false coagulum - new sutures - blood transfusion - hospitalization
- Unplanned interruption of NOAC: yes/no
- Any signs or symptoms or established diagnosis of stroke, myocardial infarction, deep vein thrombosis or pulmonary embolism
- Any non-oral bleeding
- AE and SAE assessment

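### After a Thursday extraction the permitted Friday call falls on day 1, and the day-7 bleeding question, read literally, does not reach back to the rest of that day

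*Combined protocol and SAP*

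**What the plan says.** The extraction day is day 0 (section 7.3.7), and telephone follow-up is due on days 2 and 7. Section 7.3.3 adds a weekend rule for the first call: "In case this would be a Saturday, follow-up can be performed on Friday afternoon". A call due on a Sunday may move to Monday. The bleeding questions at the first call carry no stated window. Those at the second call are headed "Bleeding assessment between day 2 and day 7" (section 7.3.4). Both calls record the date and time of any bleeding.

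Section 4.2 defines early bleeding as "any oral bleeding occurring after the extraction up to and including day 1 after the extraction" and delayed bleeding as "any oral bleeding occurring between day 2 and day 7". Minor bleeding is bleeding that needs no medical contact; one of the examples given is "clear red bleeding when spitting out the mouthwash". The primary outcome (section 4.2.1) counts oral bleeding whether early or delayed and includes minor bleeding. The protocol summary sets its period as "from randomization till end of study follow-up". Section 6.1.5 schedules three rinses a day on days 1 to 3, the last of each day in the evening.

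**The concern.** For a Thursday extraction, the permitted Friday-afternoon call takes place before day 1 has ended, and normally before that day's evening rinse. The day-7 heading repeats the words of the delayed-bleeding definition, so a caller who applies that definition would ask only about Saturday onward. The hours from the Friday call to midnight would then fall under neither set of bleeding questions.

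A patient whose only bleeding was minor and fell in those hours could be recorded as event-free on the primary outcome. Any event lost this way is an early bleed, so the proportional loss for the early-bleeding secondary outcome is at least as large as for the primary. Minor bleeding leaves little other trace:

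- The medical-file check in sections 7.1.1 and 7.3.6 applies only after unplanned medical contact.
- Patients are told to write bleeding down, but no section says the notes are collected or reviewed.
- The day-7 adverse event question might reveal such an event, but it is not a bleeding question about day 1.

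**Working it through.** **Calendar check.** Day 0 is the extraction day, and both weekend rules are applied to the first call.

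| Extraction | Day 2 falls on | First call may be made on |
|---|---|---|
| Mon | Wed | Wed, day 2 |
| Tue | Thu | Thu, day 2 |
| Wed | Fri | Fri, day 2 |
| Thu | Sat | **Fri, day 1** |
| Fri | Sun | Mon, day 3 |
| Sat | Mon | Mon, day 2 |
| Sun | Tue | Tue, day 2 |

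Thursday is the only extraction day whose first call can fall on day 1. The day-7 call for that patient is again a Thursday and is not shifted.

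**Coverage for that patient.** The first call covers extraction to Friday afternoon. On the calendar reading, the day-7 item covers Saturday (day 2) to day 7, so Friday from the call to midnight is uncovered. On the contact reading (first call to second call), nothing is uncovered.

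**The plan's own figure.** Section 10.5 gives 30% versus 15%, 80% power and 118 per group; section 10.4.1 gives two-sided 5%. The unpooled formula reproduces it: (1.960 + 0.842)² × (0.30 × 0.70 + 0.15 × 0.85) / 0.15² = 117.7, rounded up to 118.

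**Size of a possible loss.** The documents give no weekday distribution, no rate of use of the Friday option and no event times, so the following are assumptions:

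- 20% of extractions are on a Thursday: 0.20 × 236 = 47 patients.
- The Friday option is always used, the calendar reading is applied, nothing else captures the event, and the proportional loss is equal in both arms.
- The interim sample size re-estimation is ignored.

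Expected events: 118 × 0.30 + 118 × 0.15 = 35.4 + 17.7 = 53.1.

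Fraction missed m = (share of patients exposed) × (share of bleeders who bleed only in the gap). The observed rates become 0.30(1 − m) and 0.15(1 − m). Power, with n = 118 per arm, uses the pooled-variance normal formula:

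Φ{[(p₁ − p₂)√n − 1.96√(2p̄(1 − p̄))] / √(p₁(1 − p₁) + p₂(1 − p₂))}, where p̄ = (p₁ + p₂)/2.

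| Gap share assumed | Exposed | m | Events missed | Risk difference (points) | Power |
|---|---|---|---|---|---|
| None | – | 0 | 0 | 15.0 | 79.2% |
| 8 h of 7.5 × 24 = 180 h (4.4%) | 0.20 | 0.9% | 0.47 | 14.87 | 78.7% |
| 5% | 0.20 | 1.0% | 0.53 | 14.85 | 78.6% |
| 1 of 9 post-extraction rinses (11.1%) | 0.20 | 2.2% | 1.18 | 14.67 | 78.0% |
| 5%, option used for half | 0.10 | 0.5% | 0.27 | 14.93 | 78.9% |
| 11.1%, option used for half | 0.10 | 1.1% | 0.59 | 14.83 | 78.6% |
| 30% (extreme, no support in the documents) | 0.20 | 6.0% | 3.19 | 14.10 | 75.9% |

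The 11.1% row treats each bleeder as bleeding at one rinse only. Patients who bleed more than once would still be counted, so it probably overstates the loss.

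**The case against.** The strongest reply is that the day-7 heading most naturally means the interval between the two contacts. The schedule of events names those contacts by day, and the first call's bleeding questions have no window, so the calendar reading would ask about the morning of day 2 twice. Other sections point to full coverage: the protocol summary runs the outcome from randomization to the end of follow-up, the study schematic lists bleeding at day 7 without a window, section 7.1.1 assesses the prespecified outcomes at both calls, and section 10.4.2 analyses events up to day 7. A Friday-evening bleed reported on day 7 would be dated and correctly classed as early. A loss also needs several conditions to coincide, and the effect on power is less than the choice of formula: at 118 per arm the unpooled formula gives 80.1% against 79.2% pooled.

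Most of this stands. It shows that full coverage is intended, and that loss is possible rather than certain. It does not change the wording of section 7.3.4, and no section says that an early call moves the start of the day-7 recall period. Two sites could reasonably read the line differently.

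**Conclusion.** The point holds, conditionally: if the Friday option is used and the day-7 item is read as calendar days, minor bleeding late on day 1 falls under neither set of scheduled bleeding questions. In the scenarios tied to elapsed hours, rinse counts or a 5% share, the loss is about 0.5% to 2.2% of primary events and at most 1.2 percentage points of power. All of these rest on assumed weekday, usage and timing figures. With blinded arms the loss should be similar on both sides, so it would slightly shrink the risk difference rather than favour an arm, and the re-estimation in section 10.4.7.2 (150 to 300 patients) could offset part of it. This is a low-severity wording point to settle against the actual CRF. It does not threaten the trial's conclusion. It is still worth settling, because an event not asked about may not be recoverable at analysis.

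**What to change.** In section 7.3.4, replace "Bleeding assessment between day 2 and day 7" with: *Bleeding since the last completed follow-up call (state its date and time), or since the extraction if none was completed.* Check that the CRF and the call script use the same words. State that events are classed as early or delayed by the recorded date and time of bleeding, not by the call at which they were reported. This also covers a missed first call.

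The cost is one protocol line and, if needed, the matching CRF and script line. There are no extra calls, and the optional Friday call can stay as it is.
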